7.2 Subject Enrollment

Ethics Board/IRB and Medtronic approval of this Clinical Investigation Plan, the informed consent form and any other applicable documents must be obtained prior to enrolling subjects in the study. Medtronic will provide each study center with documentation of study center/investigator readiness; this letter must be received prior to subject enrollment.

When a patient and the principal investigator or authorized designee, as required, have personally signed and dated the informed consent form, the patient is considered a subject enrolled in the study. Subjects must provide informed consent before any study related procedures occur. The date the subject signed the informed consent form and data protection authorization as required by local law must be documented in the subject's medical records.

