8.5 Enrollment

A subject is considered enrolled when the consent process has been finalized. The date the subject (or the subject's authorized/designated representative or guardian) signed the IC and Data Protection

Medtronic Business Restricted

LINQ QT Study Cl	inical Investigation	Plan	
21 SEP 2022	Version 2	Page 24 of 48	Medtronic

Authorization, as required by law, must be documented in the subject's medical records. Enrollment can occur no greater than 2 years after a LINQ[™] implant, or no greater than 3 years for LINQII[™]. Subjects can also be enrolled who will be receiving a LINQ[™]/LINQII[™] implant at least 7 days prior to anti-arrhythmic drug loading.

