8.12 Subject Exit, Withdrawal or Discontinuation

Study exit is defined as the moment when a subject officially stops participating in the study. Subjects will be considered exited upon completion of the study exit e-CRF. Prior to exiting a subject from the study, it is recommended to follow the subject until any ongoing AEs are resolved/unresolved with no further actions planned, or until official study closure, whichever occurs first. The date and reason for subject exit must be reported to Medtronic at the earliest opportunity via eCRF. Exited subjects will not be replaced. Upon exiting from the study, no further study data will be collected, or study visits will occur for the subject. All data available through the time of the subject's exit will be used for analysis. Subjects are urged to remain in the study as long as possible but may be exited from the study for any of the following situations:

- Subject did not meet inclusion/exclusion criteria
- LINQ[™]/LINQII[™] ICM explanted and not replaced with a new LINQ[™]/LINQII[™] ICM (e.g., diagnosis determined, suspected infection, subject request, physician determination)
- Subject chooses to withdraw (e.g., consent withdrawal, relocation to another geographic location)
- Investigator chooses to withdraw a subject (e.g., medically justified, inclusion/exclusion criteria not met, failure of subject to maintain adequate study compliance)
- Subject lost to follow-up
- Death
- Study completion or termination

The following information/procedure is to be collected/performed at study exit:

- Date of exit
- Reason for exit

Medtronic Business Restricted

LINQ QT Study Cli	nical Investigation	Plan	
21 SEP 2022	Version 2	Page 29 of 48	Medtronic

In the case that the subject is determined to be lost to follow-up, details of a minimum of two attempts and the method of attempt (e.g., one letter and one phone record or two letters) to contact the subject must be recorded. In addition, follow the regulations set forth by the governing IRB/EC.

9. Risks and Benefits

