11.2.1 Primary Objective #1

The primary objective of the study is to determine if QT changes can be detected from LINQ[™]/LINQII[™] ECG that may occur during and after antiarrhythmic loading. The QT intervals before and after antiarrhythmic loading will be compared for all patients to analyze QT changes that may be caused due to antiarrhythmic drugs.

Medtronic Business Restricted

LINQ QT Study Clinical Investigation Plan Image: Clinical Study C

Analysis Methods: Descriptive summary statistics will be used for this objective.

Determination of Subjects/Data for Analysis: All subjects with data available will be included for this objective.

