11.3 Sample Size Determination

There are no sample size requirements as this is an observational study with no hypothesis for the study objective. A sample size of up to 20 enrolled subjects was selected assuming sufficient data can be collected from this cohort to explore the relationship between measured QT intervals from LINQ[™]/LINQII[™] before and after antiarrhythmic drug intake.

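### Does including every subject with available data let the before-loading and after-loading QT summaries describe different people?

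*Protocol*

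**What the plan says.** Only the protocol is at hand. Section 11.2.1 states the objective and then the comparison: "The QT intervals before and after antiarrhythmic loading will be compared for all patients", with the aim of analysing "QT changes that may be caused due to antiarrhythmic drugs". The method is descriptive summary statistics, and the rule on who is analysed is one sentence: "All subjects with data available will be included for this objective". Section 11.3 gives the size as up to 20 enrolled subjects, to explore how QT measurements relate "before and after antiarrhythmic drug intake". Sections 11 and 11.3 both state that there is no hypothesis.

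Three other places bear on who could have data:

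- **Entry.** Under section 7.2, once the consent form is signed and dated, "the patient is considered a subject enrolled in the study". Section 7.3 asks only that loading be scheduled. Section 8.5 also admits people who will receive an "implant at least 7 days prior to anti-arrhythmic drug loading".
- **Exit.** Section 8.12 says "Exited subjects will not be replaced" and "All data available through the time of the subject's exit will be used for analysis".
- **Measurements.** The synopsis table marks daily device transmissions from Baseline onward, but marks Holter/patch recordings and patient activations only from the index loading event. Section 6.1.8 gives the Holter's purpose in this study as collecting device ECG from which QT is measured.

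**The concern.** Enrolment precedes loading, loading is only planned at that point, and the device may already be transmitting. Someone who withdraws, loses the device or proves ineligible before loading could therefore hold data from the before period alone. Section 8.12 keeps data up to exit and rules out replacement, and the inclusion sentence in 11.2.1 sets no further condition. Taken word by word, such a person is in the analysis.

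If the before mean then came from 20 people and the after mean from, say, 16, part of the difference would reflect who contributed and not any drug effect. Two separate summaries would also hide the spread of individual changes, which bears on whether the device can show a change in a given patient. Because nothing is tested, the descriptive summary is the whole result, so its population matters.

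**Working it through.** **Step 1: the text.** The inclusion sentence is tied to this objective, and the objective is a comparison of two states in the same patients. A never-loaded subject has no loading to be before or after. A subject with readings on one side only can be listed but cannot be compared. Nothing in 11.2.1 calls for two unpaired summaries, and a table of within-subject changes is a descriptive summary. The harm requires adding a step that the protocol does not state.

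**Step 2: would before-only QT data exist?** Of the recordings at issue, only transmissions are marked at Baseline in the synopsis table. Section 6.1.7 says Home Monitor transmissions include ECG data, but no visible text says that baseline transmissions supply QT values for this analysis. Holter recordings and patient activations start at the index event. The procedural text of sections 8.6 to 8.10 and Table 2 is absent from the public version, so the question stays open; before-only QT data are possible but not established.

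**Step 3: the size, if unpaired means were used.** The protocol has no derived figure to reproduce. Inputs from section 3.1 (sotalol, QTc): 446 ± 35 ms to 474 ± 48 ms, a change of 28 ms. Assumed, because the documents give neither: k before-only subjects of 20, and a before–after correlation r of 0.3, 0.5 or 0.7.

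*Precision, complete data.* The difference of the two means is the mean of the paired differences, so both approaches have the same variance:

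(35² + 48² − 2·r·35·48)/20 = (3529 − 3360r)/20

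This gives standard errors of 11.23, 9.62 and 7.67 ms. The tempting alternative, √(35²/20 + 48²/20) = 13.28 ms, treats the same 20 people as two independent groups and is wrong.

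*Precision, k = 4.* The before mean uses 20 people and the after mean 16, all of whom are also in the before mean. Their covariance is r·35·48/20 = 84r, so:

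- available data: variance = 48²/16 + 35²/20 − 2·84r = 205.25 − 168r
- paired, n = 16: variance = (3529 − 3360r)/16

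| r | SE, available data (ms) | SE, paired n = 16 (ms) |
|---|---|---|
| 0.3 | 12.44 | 12.55 |
| 0.5 | 11.01 | 10.75 |
| 0.7 | 9.36 | 8.58 |

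Leaving out the covariance would give √205.25 = 14.33 ms and a false gap of about 3.6 ms at r = 0.5. The true gap is about 0.3 ms, and at r = 0.3 the available-data version is slightly the more precise. The chance difference between the two estimates, with SD 35·√(1/16 − 1/20) = 3.9 ms, is already contained in these standard errors.

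*Systematic shift.* If before-only subjects have a mean baseline d standard deviations above that of the others, the apparent change moves by −(k/20)·d·35 ms:

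| k of 20 | d = 0.5 | d = 1 |
|---|---|---|
| 2 | −1.75 | −3.5 |
| 4 | −3.5 | −7.0 |
| 6 | −5.25 | −10.5 |

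A lower baseline reverses the sign. For 2 of 20, the shift of 1.75 to 3.5 ms compares with a paired standard error of 7.67 to 11.23 ms even with all 20 subjects. The largest entry would make 28 ms read as 17.5 ms, but it needs 30% of subjects to be before-only, a gap of a full standard deviation, and an unpaired analysis.

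**The case for a change.** The strongest counter-argument is that 11.2.1 does more than leave a detail open. It has a line devoted to choosing subjects and data, and that line's only condition is that data exist. Section 8.12 points the same way by keeping all data up to exit. A statistical analysis plan that narrowed the set would then depart from a stated rule. Comparing for all patients can also be read as taking in everyone enrolled.

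Some of this stands. The sentence does not literally demand both readings, and a looser reading is possible. If an analyst did compare unpaired means, the shift formula above would apply, and with many before-only subjects who differ at baseline it would not be trivial.

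The conclusion does not follow, however. Section 8.12 says that data from exited subjects are not discarded; it does not say that every datum enters every summary. Requiring both readings for a change score applies the inclusion rule to a quantity that needs both, and so does not contradict it. One value per period, pairing, counts at each visit and listings of incomplete subjects are details that a protocol commonly leaves to the analysis plan. Section 11.1, on general aspects of analysis, also has no text in the public version.

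**Conclusion.** The concern does not hold. The inclusion rule is brief, but in its context it supports a sensible before-and-after comparison and does not prescribe a faulty one. The supposed distortion comes from an unpaired analysis that the protocol does not state, applied to before-only QT data whose existence the visible text does not establish.

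On precision, pairing and available data agree exactly with complete data. They differ by about 0.1 to 0.8 ms with an assumed 4 of 20 before-only subjects and r from 0.3 to 0.7. A systematic shift of 1.75 to 10.5 ms appears only under assumed counts of 2 to 6 before-only subjects and assumed baseline gaps of 0.5 to 1 standard deviation. These figures take their standard deviations from the sotalol study cited in section 3.1, not from this device. The study is exploratory, so no error rate, power statement or decision rule is affected.

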11.3 Sample Size Determination

There are no sample size requirements as this is an observational study with no hypothesis for the study objective. A sample size of up to 20 enrolled subjects was selected assuming sufficient data can be collected from this cohort to explore the relationship between measured QT intervals from LINQ[™]/LINQII[™] before and after antiarrhythmic drug intake.

11.4 Minimization of Bias

Selection of subjects, treatment of subjects, and evaluation of study data are potential sources of bias. Methods incorporated in the study design to minimize potential bias include (but are not limited to):

- Subjects will undergo screening to confirm eligibility with defined inclusion/exclusion criteria prior to enrollment.
- All sites will use the same version of the Clinical Investigation Plan and electronic case report forms (eCRFs).
- All investigational site personnel and Medtronic personnel will be trained using standardized training materials.

In summary, potential sources of bias that may be encountered in this clinical study have been considered and minimized by careful study design.

12. Ethics

12.1 Statement(s) of Compliance

The LINQ QT Study will be conducted according to the Declaration of Helsinki, Clinical Investigation Plan, Good Clinical Practice (GCP) and in accordance to the national and local laws, regulations, standards, and requirements of the countries/geographies in which the study is conducted. The principles of the Declaration of Helsinki are implemented in this study by means of the informed consent process, Ethics

Medtronic Business Restricted

LINQ QT Study Clinical Investigation Plan Image: Study Clinical Investigation Plan 21 SEP 2022 Version 2 Page 36 of 48 Mectronic

Board approval, study training, and risk benefit assessment. The sponsor shall avoid improper influence on, or inducement to, the subject, monitor, any investigator(s) or other parties participating in, or contributing to, the LINQ QT Study.

This study will be conducted in compliance with international ethical and scientific quality standards, known as good clinical practice (GCP). GCP includes review and approval by an independent IRB/Ethics Board before initiating a study, continuing review of an ongoing study by an IRB/Ethics Board and obtaining and documenting the freely given informed consent of a subject before initiating the study.

Ultimately, all sites in all geographies will follow and comply with:

- Principles of Declaration of Helsinki
- 21 CFR Part 11: Electronic Records, Electronic Signatures
- The Clinical Trial Agreement
- The procedures described within this CIP
- Local IRB/Ethics Board Requirements

In addition to the regulatory requirements outlined above, the study will be conducted according to federal, national, and local laws, regulations, standards, and requirements of the countries/geographies where the study is being conducted. These include but are not limited to the following:

In the US, the study will be conducted in compliance with:

- 21 CFR Part 50: Protection of Human Subjects
- 21 CFR Part 56: Institutional Review Boards
- 21 CFR Part 803: Medical Device Reporting

The study will not begin until IRB/EC approvals/notification, as appropriate, are received.

13. Study Administration

13.1 Monitoring

Medtronic Business Restricted

21 SEP 2022

Version 2

Medtronic

13.1.1 Monitoring Visits

13.2 Data Management

13.3 Direct Access to Source Data/Documents

The sponsor or a regulatory authority, including the FDA, may audit or inspect the study site to evaluate the conduct of the study. The clinical investigator(s)/institutions(s) shall allow study related monitoring, audits, IRB/Ethics Board review and regulatory inspection by providing direct access to source data/documents.

13.4 Confidentiality

All records and other information about subjects participating in this study will be treated as confidential. Data will be transferred and processed by Medtronic, or a third party designated by Medtronic in a key coded form, unless it's impossible to make it anonymous, for instance, where the patient's name cannot be removed from the data carrier, such as fluoroscopy images.

Medtronic Business Restricted

21 SEP 2022

Version 2

13.5 Liability/Warranty/Insurance Information

13.6 CIP Amendments

Approval of the CIP is required from the following groups prior to any study procedures at a study center:

- Medtronic
- An independent Institutional Review Board / Ethics Committee

Similarly, approval of subsequent revisions to the CIP from the above-mentioned groups is required at each study center prior to implementation of the revised CIP at that center.

13.7 Record Retention

13.7.1 Investigator Records

The investigator is responsible for the preparation and retention of the records including, but not limited to those cited below. All of the below records, with the exception of case history records and case report forms (CRFs), should be kept in the Investigator Site File (i.e., the study binder provided to the investigator) or Subject Study Binder. CRFs must be maintained and signed electronically within the electronic data capture system during the study. The following records are subject to inspection and must be retained for a period of two years (or longer as local law or hospital administration requires) after the date on which the investigation is terminated. Measures shall be taken to avoid loss or premature destruction.

- All correspondence between the IRB/EC, sponsor, monitor, regulatory authority and/or the investigator that pertains to the investigation, including required reports
- Subject's case history records, including:

- List of investigation sites
- Insurance certificates (if applicable)
 Medtronic Business Restricted

21 SEP 2022

- All approved versions of the CIP and Informed Consent Form
- Fully executed Clinical Trial Agreement
- Curriculum Vitae of principal investigator and all co-investigators/sub-investigators
- Documentation of delegated tasks
- Study training records for site personnel involved in the study
- IRB/EC approval documentation, including the IRB/EC composition where required by law, and written information that the investigator or other study staff, when member of the IRB/EC, did not participate in the approval process
- Regulatory authority correspondence, notification, and approval, where required by national legislation
- Any other records that local regulatory agencies require to be maintained
- Final Study Report including the statistical analysis

13.7.2 Sponsor Records

Medtronic shall maintain the following accurate, complete, and current records which include, but are not limited to:

- All correspondence which pertains to the investigation
- Executed Clinical Trial Agreement for all participating sites
- Curriculum vitae (signed and dated as required by local law) of principal investigator and all coinvestigators/sub-investigators at participating sites
- Documentation of delegated tasks for all participating sites
- Study training records for site personnel and Medtronic personnel involved in the study
- All approved informed consent versions, and other information provided to the subjects and advertisements, including translations
- Copies of all IRB/EC approval letters and relevant IRB/EC correspondence and IRB/EC voting list/roster/letter of assurance, if applicable
- Electronically signed and dated eCRFs
- List of names, addresses, telephone numbers and professional position of the clinical investigators and coordinating clinical investigator(s), if appointed
- Names and addresses of the institutions in which the clinical study will be conducted
- Regulatory authority correspondence, notification and approval as required by national legislation
- Names/contact addresses of monitors

Medtronic Business Restricted

21 SEP 2022

Version 2

- Monitoring reports
- Site qualification visit reports
- Statistical analyses and underlying supporting data
- Final report of the clinical study
- The Clinical Investigation Plan and study related reports, and revisions
- Sample of CRFs
- Any other records that local regulatory agencies require to be maintained

13.8 Reporting Requirements

13.8.1 Investigator Reports

The investigator is responsible for the preparation (review and signature) and submission to the sponsor of all case report forms, adverse events (reported per the country-specific collection requirements), and any deviations from the Clinical Investigation Plan. If any action is taken by an IRB/EC with respect to this clinical study, copies of all pertinent documentation must be forwarded to Medtronic in a timely manner. Reports are subject to inspection and to the retention requirements as described above for investigator records. The investigator shall prepare and submit in a complete, accurate and timely manner the reports listed in this section.

Medtronic Business Restricted

21 SEP 2022

Version	2

Page 41 of 48

Table 5: Investigator reports

Report	Submit to	Description/Constraints			
Withdrawal of IRB/EC Approval	Sponsor and Relevant Authorities if	The investigator must report a withdrawal of approval by the reviewing IRB/EC of the investigator's part of the investigation within 5			
or termination)	applicable	working days.			
Study Deviations	Sponsor and IRB/EC	Notice of deviations from the CIP to protect the life or physical wellbeing of a subject in an emergency shall be given as soon as possible, but no later than 5 working days after the emergency occurred. Reporting of all other study deviations must comply with IRB/EC policies and/or local laws and/or regulatory agency requirements and must be reported to Medtronic as soon as possible upon the center becoming aware of the deviation.			
Progress Report	Sponsor and IRB/EC and relevant authorities if applicable	The investigator must submit this report to the sponsor and IRB/EC at regular intervals, but in no event less than yearly.			
Final Report	Sponsor and IRB/EC and relevant authorities if applicable	This report must be submitted within 3 months of study completion or termination of the investigation or the investigator's part of the investigation.			

13.8.2 Sponsor Reports

Required sponsor reports are listed in Table 6 below.

Medtronic Business Restricted

21 SEP 2022

Medtronic

Page 42 of 48

Report	Submit to	Description/Constraints		
Study deviation	Investigators	Ensure that all deviations from the CIP are reviewed with the appropriate clinical investigator(s), are reported on the CRFs and the final report of the clinical investigation. Study site specific study deviations will be submitted to investigators periodically.		
Premature	IRB/EC,	Medtronic will provide prompt notification of termination or		
termination or	Investigators, and	suspension and reason(s) to investigator and where required		
suspension of clinical	regulatory	to IRB/EC and RAs.		
study	authorities, where			
	applicable			

Table 6: Sponsor reports for the United States

Version 2

13.9 Publication and Use of Information

Publications from the LINQ QT Study will be handled according to Medtronic's Policies and Standard Operating Procedures and as indicated in the CTA.

13.9.1 Publication Committee

The LINQ QT Study will utilize a Publication Committee which will include the study Principal Investigator, primary Medtronic personnel, and may include additional study investigators. This committee will manage study publications with the goal of publishing findings from the data.

The Publication Committee's role is to:

- Manage elements addressed in the publication plan as outlined in this section
- Develop the final Publication Plan under a separate cover
- Execute the Publication Plan
- Oversee the publication of primary, and ancillary study results
- Review and prioritize publication proposals
- Provide input on publication content, and
- Apply and reinforce the authorship guidelines set forth in the Publication Plan.

Membership in the Publication Committee does not guarantee authorship. The committee will meet as needed.

Medtronic Business Restricted

